3.2 Analysis Populations

3.2.1 Intent-to-Treat Population

The Intent-to-Treat (ITT) Population will include all randomized patients.

3.2.2 Modified Intent-to-Treat Population

The modified Intent-to-Treat (mITT) Population will include all patients who receive a kidney transplant from a living or deceased donor and receive at least 1 dose of study drug (6 mg/kg NPC-21, 12 mg/kg NPC-21, or placebo). The mITT Population will be used for all efficacy analyses.

3.2.3 Per Protocol Population

The Per Protocol (PP) Population will include all patients in the mITT Population who have no major protocol deviations. PP Population will be used for primary endpoint analyses. Major protocol deviations that may impact the primary efficacy assessment may include but are not limited to:

- Failed to meet eligibility criteria at randomization
- The first dose of study drug was not administered within 7 days of the kidney transplant
- The study treatment was administered out of the protocol allowed window
- Failed to receive the study treatment at scheduled visit
- Failed to complete the infusion and underdosed
- Took the wrong study drug (i.e., did not take the randomized study drug)
- Used a restricted concomitant medication not permitted per protocol
- Any other major protocol deviations

A list of subjects with major protocol deviations leading to exclusion from the PP Population will be finalized prior to unblinding the randomized treatment assignments.

3.2.4 Pharmacokinetic Population

The Pharmacokinetic (PK) Population will include all patients who receive any amount of study drug (6 mg/kg NPC-21, 12 mg/kg NPC-21, or placebo) and have evaluable PK data. The PK Population will be used for the PK analyses and exposure-response analyses.

3.2.5 Safety Population

The Safety Population will include all randomized patients who receive at least 1 dose of study drug (6 mg/kg NPC-21, 12 mg/kg NPC-21, or placebo). The Safety Population will be used for safety analyses.

3.3 Patient Data and Study Conduct

3.3.1 Patient Disposition

The following patient disposition categories will be summarized via counts and percentages by treatment group and in total for all screened patients:

- Patients who were screened
- Patients who were randomized
- Patients who were treated
- Patients who end study treatment and continued in the study for assessments
- Patients who end study treatment but discontinued in the study for assessments
 - Primary reason for discontinuation
- Patients who completed the study
- Patients who withdrew early from the study
 - Withdrew early from the study before Week 16
 - Withdrew early from the study after Week 16
 - Primary reason for early withdrawal
- Patients who entered rescue phase
 - Reason for entering rescue phase

All patient disposition data will be listed by-patient.

3.3.2 Protocol Deviations

Counts and percentages of patients with protocol deviations by CSR reportable deviation category will be summarized by treatment group and in total based on the ITT Population. Descriptions and categories of CSR reportable events are found in the Protocol Deviation Plan.

Protocol deviations in study procedures due to COVID-19 will be reported in the CSR. All protocol deviations data will be listed by-patient.

3.3.3 Analysis Populations

Counts and percentages of patients in each analysis population will be summarized by treatment group and in total based on all randomized patients.

All analysis population data will be listed by-patient.

3.3.4 Demographic and Baseline Characteristics

The following demographic and baseline characteristics will be summarized:

- Country (United States, Japan)

- Age (Years)
- Age group (< 65, ≥ 65)
- Sex (Male, Female)
 - Childbearing potential
- Ethnicity (Hispanic or Latino, Not Hispanic or Latino, Not Reported, Unknown)
- Race (American Indian or Alaska Native, Asian, Black or African American, Native Hawaiian or Other Pacific Islander, White, Other: Specify)
- Height (cm)
- Weight at pre-randomization (kg)
- Weight group (< 100 kg, ≥ 100 kg)
- Body mass index (kg/m²)
- Time from transplantation to first dose date(days)
 - Day = First dose date of study drug – date of kidney transplant + 1.
- Primary disease (Diabetic Kidney Disease, Glomerulonephritis, Polycystic Kidney Disease, Other, Not Specified, Unknown)
- Donor status (Deceased, Living)
- ABO compatibility (Compatible, Incompatible)
- Dialysis introduction (Yes, No)
 - Dialysis specify (Hemodialysis, Peritoneal Dialysis)
- Central CMV DNA level (IU/mL) at baseline
- Induction therapy (Yes, No), if yes, summarize by the below categories:
 - Alemtuzumab
 - ATG (Thymoglobulin®)
 - Rituximab
 - Basiliximab
 - Bortezomib
 - Eculizumab
- Immunosuppressive agents at randomization (Azathioprine, Belatacept, Cyclosporine, Everolimus, Gusperimus, MMF, Sirolimus, Steroids, Tacrolimus)

Demographic and baseline characteristics will be summarized with descriptive statistics or counts and percentages of patients as appropriate by treatment group and in total for all defined analysis populations.

3.3.5 Medical History

Counts and percentages of patients who experienced any past and/or concomitant diseases, and counts and percentages of patients who experienced any past surgeries will be summarized by treatment group and in total.

Medical history will be coded to system organ class (SOC) and preferred term (PT) using the Medical Dictionary for Regulatory Activities (MedDRA) v24.0. Counts and percentages of patients with medical history by SOC and PT will be summarized by treatment group and in total based on Safety Population.

All medical/surgical history data will be listed by-patient.

3.3.6 Prior and Concomitant Medications

Concomitant medications will be coded to anatomical therapeutic chemical (ATC) class and PT using the WHO Drug Global B3, March 2021. Medications will be considered as prior medications if they stopped prior to the first dose of study drug and concomitant medications if they were taken at any time after the

first dose of study drug (i.e., started prior to the first dose of study drug and were ongoing, or started after the first dose of study drug).

If a medication has incomplete start or stop dates, dates will be imputed to determine whether a medication should be considered prior or concomitant. If a medication start date is incomplete, the first day of the month will be imputed for missing day and January will be imputed for missing month. If a medication stop date is incomplete, the last day of the month will be imputed for missing day and December will be imputed for missing month. Incomplete start and stop dates will be listed as collected without imputation.

Counts and percentages of patients taking prior and concomitant medications by ATC class and PT will be summarized by treatment group and in total based on the Safety Population, separately. Patients will be counted only once by medication class or name.

All prior and concomitant medications will be listed by-patient.

3.3.7 Study Drug Exposure

The duration of study drug will be calculated as:

- Duration of study drug (days) = last dose date of study drug + 28 – first dose date of study drug

Total volume administered (mL):

- Total volume administered (mL) = cumulative volume of study drug administered up to last dose

Total study drug administered (mg):

- Total study drug administered (mg) = $10 \times$ Total volume administered (mL)

Duration of study drug, total study drug administered (mg), and the count and percentages of number of infusions administered (e.g., 1, 2, 3, 4) will be summarized by treatment group.

In addition, for each scheduled visit (e.g., Day 1, Day 29, Day 57, and Day 85), the proportion of patients who receive the treatment among patients who are expected to receive the treatment will be summarized. For each visit, the patients who withdraw from the treatment or enter the rescue phase by this visit will be excluded from the analysis.

All study drug exposure data will be listed by-patient.

3.4 Efficacy Assessment

The mITT Population will be used for efficacy analyses. The primary efficacy endpoint will also be analyzed on the PP Population.

3.4.1 Primary Efficacy Analysis

The proportion of patients with the occurrence of CMV disease (CMV syndrome [see Appendix C of the protocol for definition of CMV syndrome] or tissue-invasive CMV disease [see Appendix D of the protocol for definitions of CMV disease]) or CMV viremia (defined as the detection of ≥ 250 IU/mL in plasma measured by PCR analysis in central laboratory or meets the local criteria for CMV viremia measured by PCR analysis or antigenemia testing) by Week 16 will be summarized by treatment group.

The 2-sided 95% exact Clopper-Pearson confidence intervals of the proportions will be provided. For any two treatment groups, the proportion difference and 95% unstratified Miettinen-Nurminen (score) confidence limits will be presented.

Comparisons across placebo and 6 mg/kg NPC-21 treatment group will use logistic regression analysis with stratification factor of region (United States or Japan) as a covariate

Non-responders will include all patients who develop CMV disease or CMV viremia. In principle, patients who discontinue from the study prior to Week 16 in the absence of CMV disease or CMV viremia will be considered as non-responders. If warranted under special circumstances, a patient who discontinues from the study prior to Week 16 may be discussed with the medical expert to determine status as a responder or non-responder. If this occurs, the rationale for considering the patient as a responder will be finalized before database lock and documented in this SAP. Sensitivity analysis may be performed to assess the impact of these patients on analysis results.

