10.2 Statistical Methods

10.2.1 Analysis of Efficacy

The mITT Population will be used for all efficacy analyses.

The primary efficacy endpoint will be the proportion of patients with the occurrence of CMV disease (CMV syndrome [see Appendix C for definition of CMV syndrome] or tissue-invasive CMV disease [see Appendix D for definitions of CMV disease]) or CMV viremia (defined as the detection of ≥ 250 IU/mL in plasma measured by PCR analysis in central laboratory or meets the local criteria for CMV viremia measured by PCR analysis or antigenemia testing) by Week 16. Non-responders will include all patients who develop CMV disease or CMV viremia. In principle, patients who discontinue from the study prior to Week 16 in the absence of CMV disease or CMV viremia will be considered as non-responders. If warranted under special circumstances, a patient who discontinues from the study prior to Week 16 may be discussed with the medical expert to determine status as a responder or non-responder. If this occurs, the rationale for considering the patient as a responder will be finalized before database lock and documented in the Statistical Analysis Plan. Sensitivity analysis may be performed to assess the impact of these patients on analysis results.

The primary efficacy endpoint will be summarized by treatment group and compared across placebo and the 6 mg/kg NPC-21 treatment group using a logistic regression analysis with stratification factor of region (United States or Japan) as a covariate.

Other efficacy endpoints will be summarized descriptively by treatment group using the mITT Population.

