2.2 Study Design

2.2.1 Overview

This is a Phase 2, randomized, double-blind, placebo-controlled study of NPC-21 for kidney transplant recipients at high risk of CMV infection at approximately 25 clinical sites in the United States and Japan. Approximately 108 eligible patients will be randomized in a 4:1:4 ratio prior to first study drug administration to receive 6 mg/kg NPC-21, 12 mg/kg NPC-21, or placebo. Randomization will be stratified by region (United States or Japan).

Figure 1 displays a schematic of the study's design.

Figure 1. Study Schematic

*When the patient meets the primary endpoint, the patient move to the rescue phase

Adult CMV seronegative patients receiving a first kidney transplant from CMV seropositive donors will be enrolled in the study. Participation in the study will consist of a Screening Period (up to 14 days prior to first study drug administration), a 16-week Treatment Period, and a 12-week Observation Period. The total duration of the study (including Screening, Treatment Period, and Observation Period) will be approximately 30 weeks. After first study drug administration, patients who develop detectable CMV disease (CMV syndrome or tissue-invasive CMV disease) or CMV viremia (defined as the detection of ≥ 250 IU/mL in plasma measured by polymerase chain reaction [PCR] analysis in central laboratory or meets the local criteria for CMV viremia measured by PCR analysis or antigenemia testing) can enter the Rescue Phase of the study and be treated by anti-CMV agents per local standard of care until the patient is negative for CMV viremia, has recovered from CMV disease, or up to Week 28, whichever comes first. When this rescue therapy is completed, the Rescue Phase is terminated at least 4 Study Weeks after the last study drug administration and all Week 28 procedures will be performed as per Section 6.7 the Early Termination Visit and Withdrawal Procedures of the protocol.

The 16-week Treatment Period will include study drug administration on Day 1 and at Weeks 4, 8, and 12. The 16-week Treatment Period will begin as soon as practical post-transplant but no later than 7 days post-transplant.

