2.2.4 Sample Size Determination

A total sample size of approximately 108 patients is planned for the study, with a 1:1 randomization ratio for 6 mg/kg NPC-21 versus placebo and another 12 patients for high-level dose of 12 mg/kg NPC-21 (4:1:4 randomization ratio for 6 mg/kg NPC-21, 12 mg/kg NPC-21, or placebo). The sample size calculation is based on the modified Intent-to-Treat (mITT) Population from the first dose of NPC-21 through Week 16 for the occurrence of CMV disease (CMV syndrome or tissue-invasive CMV disease) or CMV viremia (defined as the detection of ≥ 250 IU/mL in plasma measured by PCR analysis in central laboratory or meets the local criteria for CMV viremia measured by PCR analysis or antigenemia testing) primary endpoint. Assuming an early discontinuation rate of 15%, approximately 48 patients each in the 6 mg/kg NPC-21 and placebo arms are needed with a 2-sided significance level of 0.05 and a power of 80% to detect a difference between NPC-21 at a predicted incidence rate of CMV disease (CMV syndrome or tissue-invasive CMV disease) or CMV viremia of 30% versus 60% for placebo. In addition, a sample size of 12 patients for the 12 mg/kg NPC-21 arm is considered adequate for the planned exposure-response analysis.

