3.4.2 Secondary Efficacy Analysis

3.4.2.1 Categorical Endpoints

The categorical endpoints as below will be analyzed using the same analysis method as primary analysis:

- Incidence of CMV disease or CMV viremia by Week 28
- Incidence of CMV disease by Week 16
- Incidence of CMV disease by Week 28
- Incidence of CMV viremia by Week 16
- Incidence of CMV viremia by Week 28
- Incidence of anti-CMV therapy during the Rescue Phase

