3.4.2.3 Time-to-Event Endpoints

The time-to-event endpoints include:

- Time to detectable CMV disease or CMV viremia by Week 28
- Time to detectable CMV disease by Week 28
- Time to detectable CMV viremia by Week 28

For each time-to-event endpoint, the count and proportion of patients experiencing event and censored will be summarized by treatment group. The Kaplan-Meier estimate of median time and Brookmeyer-Crowley 95% confidence intervals will be presented. Log-rank test will be used to test whether there is significant difference among groups.

The endpoints will be calculated as:

- Time to detectable CMV disease or CMV viremia by Week 28 (Weeks) = (Date of CMV disease or CMV viremia – first dose date of study drug + 1)/7.
- Time to detectable CMV disease by Week 28 (Weeks) = (Date of CMV disease – first dose date of study drug + 1)/7.
- Time to detectable CMV viremia by Week 28 (Weeks) = (Date of CMV viremia – first dose date of study drug + 1)/7.

If patients experience CMV disease or CMV viremia, the dates of entering Rescue Phase will be used to determine the date of CMV disease or CMV viremia and the patients will not be censored. Patients who do not experience CMV disease or CMV viremia will be censored at the latest CMV viremia assessments.

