A complete physical examination will be performed at Screening; prior to study drug administration on dosing days (Day 1 and at Weeks 4, 8, and 12); within 1 hour of the end of the infusion on Day 1; at Weeks 1, 2, 3, 16, 20, 24, and 28; and at the initiation of the Rescue Phase. A physical examination may be performed by home healthcare services at non-dosing day visits.

The physical examination will be presented in a by-patient listing.

3.7.6 *Data Safety Monitoring Board*

The Data Safety Monitoring Board (DSMB) will meet to review unblinded aggregate and individual patient data related to safety, data integrity, and overall conduct of the study and will provide recommendations to continue, temporarily halt, modify, or terminate the study based on data analysis. The committee may communicate other recommendations or concerns as deemed appropriate. Additional information will be provided in the DSMB charter as approved by the members.

3.8 **Interim Analysis**

No interim analysis is planned.

4 **CHANGES FROM PROTOCOL-SPECIFIED STATISTICAL ANALYSES**

In Section 3.4.2.2 for secondary efficacy analysis, the below secondary analysis was added compared to protocol:

- Duration of the detection of CMV DNA ≥ 250 IU/mL in plasma measured by PCR analysis in central laboratory.

The section 3.4.3 was added as the exploratory analysis to the endpoints.

5 **PROGRAMMING SPECIFICATIONS**

Analyses will be performed using SAS® version 9.3 or higher. All available data will be presented in patient data listings which will be sorted by patient and visit date as applicable. Detailed Programming Specifications will be provided in a separate document.

STATISTICAL ANALYSIS PLAN ADDENDUM

Protocol Title: A Phase 2, Randomized, Double-Blind, Placebo-Controlled Study of NPC-21 for Kidney Transplant Recipients at High-Risk of Cytomegalovirus Infection (LionHeart21)

Protocol Number: NPC-21-2

Protocol Version/Date: Version 5.0/18 October 2021

Investigational Product: NPC-21

Sponsor: Nobelpharma Co., Ltd.
[name]
[name]
[contact]
[contact]

SAP Version/Date: Version 1.0/29 March 2023

SAP Addendum Version/Date: Version 1.0/15 May 2023

CONFIDENTIAL

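### The risk-difference interval ignores the randomisation stratum that the primary model adjusts for, and the log-rank test names no pair of arms

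*SAP*

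**What the plan says.** Randomisation is stratified by region (SAP 2.2.1 and 2.2.2; Protocol 5.3). For the primary endpoint, SAP 3.4.1 compares placebo with 6 mg/kg by "logistic regression analysis with stratification factor of region (United States or Japan) as a covariate". In the same section the absolute effect is described differently: "For any two treatment groups, the proportion difference and 95% unstratified Miettinen-Nurminen (score) confidence limits will be presented".

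SAP 3.4.2.1 carries the method to six secondary endpoints: "The categorical endpoints as below will be analyzed using the same analysis method as primary analysis".

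For the three time-to-event endpoints, SAP 3.4.2.3 says: "Log-rank test will be used to test whether there is significant difference among groups". It names neither the arms nor any strata.

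Three other places bear on this:

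- Protocol 10.2.1 names one efficacy comparison, 6 mg/kg versus placebo, and then says: "Other efficacy endpoints will be summarized descriptively by treatment group using the mITT Population".
- SAP 2.2.4 gives the third arm a limited role: "a sample size of 12 patients for the 12 mg/kg NPC-21 arm is considered adequate for the planned exposure-response analysis".
- SAP section 4 records two changes from the protocol: an added duration-of-viremia analysis, and "The section 3.4.3 was added as the exploratory analysis to the endpoints". The log-rank test is not among them.

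The SAP addendum of 15 May 2023 changes only how early discontinuations are counted. It leaves all of the above as it stands.

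**The concern.** **Interval.** The unstratified risk difference is the only absolute between-group estimate planned for the primary endpoint. It is reported beside a test that adjusts for region. If region predicts the event, the unstratified interval counts between-region variation as noise although the stratified design has balanced it between the arms. The interval is then too wide, and a report could show a significant primary test next to a difference whose limits include zero.

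A regional difference is plausible from the documents. One route to viremia is each site's local criteria. Protocol 7.3 also lets home-healthcare visits, available only in the United States, omit the local sample. The size of any difference is unknown.

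**Log-rank test.** The natural reading is an unstratified three-group test, although this is not written. Such a test does not target the one comparison the protocol names, and it brings in a 12-patient arm sized for exposure-response work. A significant result could be misread as evidence for 6 mg/kg. It is also an inferential test on endpoints that the protocol calls descriptive, and it is not declared as a change.

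**Working it through.** **Inputs from the documents (SAP 2.2.4).** Two-sided alpha 0.05, power 80%, event rates 30% and 60%, 15% discontinuation, about 48 patients in each main arm and 12 at 12 mg/kg.

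**Assumptions (not in the documents).** The regional split and the strength of the region effect, both shown as ranges.

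**1. The plan's own figure.** With unpooled variance, n = (1.96 + 0.8416)² × (0.6×0.4 + 0.3×0.7) / 0.3² = 39.24, rounded up to 40. Then 40/0.85 = 47.06, rounded up to 48. The stated 48 per arm reproduces.

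**2. Interval width, by hand.** Take a 50:50 regional split, a regional risk gap g in both arms and a constant risk difference.

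- Unstratified half-width: 1.96 × √[(0.24 + 0.21)/48] = 0.190.
- Stratified half-width: 1.96 × √[(0.45 − 0.5g²)/48].

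| Regional gap | Stratified / unstratified width |
|---|---|
| 0 points | 1.000 |
| 10 points | 0.994 |
| 20 points | √(0.43/0.45) = 0.978 |
| 30 points | 0.949 |
| 40 points | √(0.37/0.45) = 0.907 |

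So the unstratified interval is about 2% too wide at 20 points (1/0.978) and about 10% at 40 points (1/0.907).

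**3. The Miettinen-Nurminen intervals, by simulation.** The stratified version uses Mantel-Haenszel weights. Setting: 48 per arm, 60% versus 30%, regional splits of 50:50, 75:25 and 25:75, and a logistic Wald test with region as covariate. There were 50,000 trials per setting for discordance and 2,000 for width.

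| Region odds ratio | Excess width of unstratified interval | Primary test significant, unstratified interval includes zero |
|---|---|---|
| 1 | 0% | 0.0% |
| 2 | about 1% | 0.1–0.2% |
| 4 | 3–5% | 0.8–1.7% |
| 8 | 5–10% | 2.4–3.9% |

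With the stratified interval the last column is 0.0% in every setting. The reverse disagreement (stratified interval excludes zero, logistic test not significant) occurs in at most 0.16% of trials. At 60% versus 40% (50:50 and 75:25 splits; 20,000 trials) the unstratified discordance is 0.0%, 0.1–0.2%, 1.5–3.0% and 5.3–9.0%.

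Coverage at gaps of 0, 20 and 40 points (50:50 split, 1,500 trials each) was 94.1%, 94.8% and 96.6% unstratified, against 94.1%, 94.7% and 95.1% stratified. The unstratified interval errs on the conservative side.

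**4. A worked case.** Suppose 6 mg/kg has 4/24 and 14/24 events in the two regions, and placebo 8/24 and 19/24. The fitted region odds ratio is 7.3. The difference is 18/48 − 27/48 = −18.75 points with either method.

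- Logistic test with region: p = 0.044.
- Unstratified Miettinen-Nurminen: −37.4 to +1.3 points.
- Stratified Miettinen-Nurminen: −36.0 to −0.6 points.

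A Wald check by hand shows the same pattern. The unstratified standard error is √[(0.2344 + 0.2461)/48] = 0.1000, giving −38.4 to +0.9. The stratified standard error is ½√[(0.1389 + 0.2222)/24 + (0.2431 + 0.1649)/24] = 0.0895, giving −36.3 to −1.2.

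**5. Log-rank test.** Setting: 10,000 trials each, 48:12:48, weekly event times, 15% dropout per 16 weeks, follow-up to Week 28, no region effect.

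| Incidence: placebo / 6 / 12 mg/kg | Three-group test rejects | 6 mg/kg vs placebo rejects |
|---|---|---|
| 60 / 60 / 30% | 44.6% | 5.3% |
| 60 / 60 / 45% | 12.5% | 4.9% |
| 60 / 30 / 30% | 90.6% | 92.6% |
| 60 / 30 / 60% | 91.3% | 92.9% |
| 60 / 30 / 15% | 97.6% | 93.0% |

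If the regional hazard ratio is 2 at 60/30/30, stratifying the pairwise test raises its power from 92.3% to 93.8%.

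**The case against.** The strongest reply is that nothing here is an error.

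- **The interval is openly labelled and valid.** It estimates a legitimate marginal difference and, if anything, over-covers. This stands, and it is why the point is an improvement rather than a correction.
- **The gain is small unless region is strongly prognostic.** At a 50:50 split, an odds ratio of 4 means regional gaps of about 32 points (placebo) and 28 points (6 mg/kg), and an odds ratio of 8 about 45 and 38. The documents support no particular size. This also stands, and the worked case was chosen near p = 0.05.
- **SAP 3.4.4 already plans results by country, if the data allow.** That gives separate regional estimates, but not a pooled difference that respects the strata.
- **The three-group reading is not written, and programming specifications are deferred to a separate document.** That document may settle the pair and strata, but a reader of the SAP cannot tell. Kaplan-Meier results by arm would help show which arm drives a result.
- **The 45% is not a false-positive rate.** In that scenario 12 mg/kg does work, so rejecting overall equality is correct. Power at the planned effect hardly differs. Both are true. The difficulty is which question the test answers.
- **SAP section 4 also omits the logistic comparisons of secondary endpoints.** This is correct and adds to the documentation gap.

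The simulations cover 60% versus 30% and 60% versus 40% only. Low-incidence outcomes, such as CMV disease alone, were not examined.

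**Conclusion.** The concern holds, as a low-cost improvement with limited impact. The interval for 6 mg/kg versus placebo omits the factor that the trial randomises by and the primary model adjusts for. The cost depends wholly on how prognostic region is: none if it is not, about 1% of width at an odds ratio of 2, and up to about 10% at 8, with a contradictory test and interval in at most 3.9% of trials at the planned rates. These sizes rest on assumed regional splits and effects.

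The log-rank point rests on the wording alone: the comparison and strata are unstated, and a three-group result would not isolate 6 mg/kg. Its absence from SAP section 4 needs no assumption.

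**What to change.** 1. **SAP 3.4.1, and 3.4.2.1 where it reuses the method:** report the region-stratified Miettinen-Nurminen interval for 6 mg/kg versus placebo. Keep the unstratified interval as supportive, and for pairs involving the 12-patient arm, where regional strata would be sparse.
2. **SAP 3.4.2.3:** state that the log-rank test compares 6 mg/kg with placebo, stratified by region, and present 12 mg/kg descriptively.
3. **SAP section 4:** list the log-rank test as a change from the protocol's descriptive plan. The logistic comparisons of secondary endpoints belong there for the same reason.

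Before lock this costs only wording and standard software options, with no added patients or data. The one trade-off is that the pairwise log-rank test gives up some power to detect any difference if 12 mg/kg outperforms 6 mg/kg (93.0% against 97.6% at 60/30/15). The addendum dates the database lock to 30 March 2023. For this trial the stratified interval and pairwise test would therefore be supplementary analyses, labelled as post-lock and documented in the clinical study report as the SAP Introduction requires.

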2.2.2 Randomization

At Screening, a unique patient identification number will be established for each patient who has provided written informed consent. This patient identification number will be used for patient identification throughout the study and in all study-related documentation. This will be a 5 digit hyphenated number of the following format: XYY-ZZ, where X is the country number (1 [US] or 2 [Japan]), YY is the sequential unique site identification number, and ZZ is a sequential unique number assigned to the patient at that site.

Each patient number will be assigned only once and will not be reassigned to another patient if a patient fails during Screening. Interactive Response Technology (IRT) will not allow repeat of numbers. This unique identifier will be used in all study documentation for that patient from first to last contact.

After informed consent and body weight are obtained, pre-Randomization will take place via the IRT system to 1 of 3 treatment groups (6 mg/kg NPC-21, 12 mg/kg NPC-21, or placebo) in a 4:1:4 ratio. Randomization will be stratified by region (United States or Japan). Randomization will take place prior to first study drug administration after confirming all criteria. Randomization procedures may occur on Day -1 or Day 1 prior to first study drug administration.

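### The only planned risk-difference interval for the primary endpoint ignores the randomisation stratum: valid, but somewhat conservative if event rates differ by region (minor)

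*SAP*

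**What the plan says.** SAP 2.2.2 and Protocol 5.3 stratify randomisation by region, with two levels. For the primary comparison of 6 mg/kg with placebo, SAP 3.4.1 specifies "logistic regression analysis with stratification factor of region (United States or Japan) as a covariate", and Protocol 10.2.1 has the same model.

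For the difference in proportions, SAP 3.4.1 says: "For any two treatment groups, the proportion difference and 95% unstratified Miettinen-Nurminen (score) confidence limits will be presented". The protocol specifies no risk-difference interval. The SAP addendum of 15 May 2023 changes how discontinuations are counted for some endpoints but adds no stratified or standardised interval. The documents also do not say which estimate and interval the logistic model will report.

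The 3.4.1 method is reused for the six categorical secondary endpoints (SAP 3.4.2.1), for the primary endpoint in the Per Protocol Population (SAP 3.4), and for the reviewer-assessed and central-PCR-only analyses (SAP 3.4.3).

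The sample size is set on the proportion scale, "CMV viremia of 30% versus 60% for placebo": "Assuming an early discontinuation rate of 15%, approximately 48 patients each in the 6 mg/kg NPC-21 and placebo arms are needed".

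**The concern.** The p-value and the interval for the same comparison come from analyses that treat the design differently. Stratified randomisation balances region between the arms. If region is prognostic, the between-region variation is then no longer part of the error in the treatment difference. The logistic model takes account of this; the unstratified interval still counts that variation as noise.

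Two things could follow. The interval could be wider than the design supports, and one table could show an adjusted p-value below 0.05 beside an interval that contains zero. This matters for presentation because the trial is sized on a difference in proportions, and this is the only between-group interval that the SAP names for the primary endpoint.

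**Working it through.** **1. The plan's own figure.** Inputs from SAP 2.2.4: 30% versus 60%, two-sided 0.05, 80% power, 15% discontinuation, 1:1 for this pair. With unpooled variance,

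n = (1.960 + 0.842)² × (0.30×0.70 + 0.60×0.40) / 0.30² = 7.849 × 0.45 / 0.09 = 39.2, so 40 per arm; 40 / 0.85 = 47.1, so 48.

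The stated 48 is reproduced. Patients who discontinue before Week 16 count as non-responders (SAP 3.4.1), so all 48 per arm are used below.

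**2. How much width the stratum is worth.** The documents give neither the US/Japan split nor region-specific rates, so both are assumed. Let g be the gap in event rate between regions, equal in both arms, and f the share of patients in one region. The binomial variance in each arm is the within-region part plus f(1−f)g². The stratified interval drops the second part, so approximately

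width ratio (unstratified / stratified) = √{0.45 / [0.45 − 2f(1−f)g²]}.

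| Gap g | f = 0.50 | f = 0.75 |
|---|---|---|
| 0 | 1.000 | 1.000 |
| 20 points | √(0.45/0.430) = 1.023 | √(0.45/0.435) = 1.017 |
| 30 points | √(0.45/0.405) = 1.054 | √(0.45/0.41625) = 1.040 |
| 40 points | √(0.45/0.370) = 1.103 | √(0.45/0.390) = 1.074 |

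**3. Simulation with the actual intervals.** The Miettinen-Nurminen limits are the values δ at which (d − δ)²/V(δ) = 3.84. In the stratified version d = Σwᵢ(p₁ᵢ − p₂ᵢ), with Mantel-Haenszel weights wᵢ proportional to n₁ᵢn₂ᵢ/(n₁ᵢ + n₂ᵢ), and V(δ) = Σwᵢ²[p̃₁ᵢ(1−p̃₁ᵢ)/n₁ᵢ + p̃₂ᵢ(1−p̃₂ᵢ)/n₂ᵢ]·Nᵢ/(Nᵢ−1), where p̃ are the restricted maximum-likelihood rates. The test is the Wald test from the region-adjusted logistic model. Each scenario had 1,500 trials, 48 per arm, at 30% versus 60%.

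| Split | Gap | Mean width, unstratified | Mean width, stratified | Unstratified wider by | Adjusted p<0.05 but unstratified interval includes 0 |
|---|---|---|---|---|---|
| 50:50 | 0 | 0.371 | 0.371 | 0% | 0% |
| 50:50 | 20 | 0.371 | 0.364 | 2.0% | 0.4% |
| 50:50 | 30 | 0.371 | 0.354 | 4.9% | 1.5% |
| 50:50 | 40 | 0.372 | 0.340 | 9.3% | 4.1% |
| 75:25 | 0 | 0.371 | 0.371 | 0% | 0% |
| 75:25 | 20 | 0.371 | 0.366 | 1.5% | 0.3% |
| 75:25 | 30 | 0.372 | 0.359 | 3.5% | 0.9% |
| 75:25 | 40 | 0.372 | 0.349 | 6.6% | 2.6% |

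The simulation agrees with step 2. Coverage of the unstratified interval was 94–96%, highest (96%) at the 30- and 40-point gaps. The stratified interval never included zero when the adjusted p was below 0.05. At a smaller true effect (40% versus 60%) conflicts are more frequent: 2.6% for a region odds ratio of 4, and up to 6.8% at a 40-point gap.

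**4. One data set showing the conflict** (assumed counts, 24 per region per arm). 6 mg/kg: 5/24 and 15/24. Placebo: 9/24 and 20/24. Pooled: 20/48 versus 29/48, difference −18.8 points.

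- Region-adjusted logistic model: log odds ratio −0.956, standard error 0.475, Wald p = 0.044 (likelihood ratio p = 0.040).
- Unstratified Miettinen-Nurminen: −37.4 to +1.4 points.
- Region-stratified Miettinen-Nurminen: −36.0 to −0.6 points.

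Simple Wald variances show the reason. Unstratified: 0.2431/48 + 0.2391/48 = 0.01005, standard error 0.1002. Stratified: 0.25 × (0.1649 + 0.2344 + 0.2344 + 0.1389)/24 = 0.00805, standard error 0.0897. The estimate is the same and only the error term differs.

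With the same totals and no regional difference (10/24 and 10/24 versus 14/24 and 15/24), p = 0.068, the unstratified interval is −37.4 to +1.4 and the stratified one −37.5 to +1.5. Nothing conflicts and nothing is gained.

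**The case against.** The case for leaving the plan alone has real substance.

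- **No inference depends on the interval.** It is presented for every pair of arms; the hypothesis is tested in the model that already adjusts for region. This stands.
- **The interval is valid.** Ignoring a prognostic stratum after stratified randomisation errs, if at all, towards conservatism. This stands. A reader might infer that the primary result or its error rate is compromised; the documents do not support that.
- **The gain is conditional.** A reader might also infer that the interval is wider than it need be whatever the data. That does not follow. Without a regional gap the mean widths are equal, and in a single data set the stratified interval can be slightly the wider one. The documents offer reasons why region could matter: viremia may be called by local criteria, and home healthcare, which waives the local sample, exists only in the United States. They give no rates, so the larger figures rest on large assumed gaps.
- **The sample size is itself unstratified**, so the planned interval matches the planning formula. True, but the analysis then adjusts for region, and the interval beside it does not.
- **One method for all pairs is tidy, and subgroup results by country are planned** (SAP 3.4.4). For pairs involving the 12-patient arm, regional strata would be very small and the unstratified interval is reasonable. This does not apply to 48 versus 48, and subgroup results do not supply an overall interval consistent with the test.

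**Conclusion.** There is a minor mismatch between design and presentation. The only risk-difference interval for 6 mg/kg versus placebo ignores the factor that both the randomisation and the primary model use. At the planned effect with 48 per arm, it is about 2% wider than the region-stratified interval at an assumed 20-point gap, 4–5% at 30 points and 7–10% at 40 points, with no difference in mean width when there is no gap. It includes zero despite a significant region-adjusted test in about 0–4% of simulated trials. These sizes rest on assumed regional splits and gaps, equal gaps in both arms, and a Wald test, since the SAP does not name the test statistic. The primary test, type I error and sample size stand as planned.

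**What to change.** For 6 mg/kg versus placebo, report the Miettinen-Nurminen difference and 95% interval stratified by region with Mantel-Haenszel weights, for the primary endpoint and each endpoint that inherits the 3.4.1 method. Keep the unstratified interval for pairs involving the 12 mg/kg arm. In the same text, name the odds ratio and interval to be reported from the logistic model.

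The SAP was finalised on 29 March 2023 and the database locked on 30 March 2023, so the stratified interval should not replace the planned one. Add it beside the planned interval by documented addendum, labelled as added after lock, and record it in the Clinical Study Report as SAP section 1 requires.

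The cost is a short addendum, one program option and an extra row in the affected tables. No new data are needed.
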